- **Day 0:** On the following day each subject will collect their baseline (day 0) stool and urine samples (Fig. 1). They will visit the CAB building to have a blood sample (2 tablespoons or 30 mL) drawn by a study nurse. Blood will be used for CMP test and prepared serum will be aliquoted and stored at -80 °C until processing for marker analysis and metabolomics. Analysis of day 0 samples should help isolate any effects due to SPI alone from subsequent samples collected during GP-SPI intervention. On day 0 subjects will drop off urine and stool samples at IFNH and collect GP-SPI packets. On Day 0 participants will also take a break from consuming SPI and will start GP-SPI supplementation on morning of Day 1.
- **GP-SPI (Day 1 – 10):** Each subject will receive twenty pre-weighed 20 g packets of GP-SPI. On day 1 subjects will be instructed to mix each packet of GP-SPI in 250 mL of water or in smoothie (recipe example will be provided, please see below) using allowed foods as detailed in instructions and consume the GP-SPI mix once in the morning before breakfast and once in the evening before dinner for 10 consecutive days (Fig. 1).

- Subjects will be provided with a personal blender for smoothie preparation (value ~ \$25) that they can keep.
- **Digital food diary:** Participants will be asked to take photos of all their food and drink (except water) including the study supplements with their personal mobile computing device (e.g. smart phone, iPad, or similar). Participants will be required to download the free mobile app WhatsApp to send photos with a brief description of the food items. Photos and food description may also be sent to an email address that will be created for this study ([contact]). The food diary must be kept over the 5-day SPI and wash-out period, day 0 (break day), the 10-day GP-SPI intervention period, and up until the final blood draw on day 11 (17 days total).

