- **Bristol stool scale form:** Subjects will be provided with the Bristol stool scale (BSS) form and asked to complete it for stool samples they collect on days -5, 0, 2, 4, 6, 8, and 10 of the study. Stool consistency has been shown to strongly correlate with gut microbiota richness and composition, enterotypes, and bacterial growth rates (17). Self-assessed stool consistency as categorized by the BSS is used in clinical studies as a proxy for colonic transit rate. The BSS classifies human feces into 7 consistency categories. The highest scores (6 - 7) correspond to loose stools and fast transit time (i.e. diarrhea), while lower scores (1 - 2) correspond to hard stools and longer colon transit time (i.e. constipation). Scores between 3 – 5 are reflective of easily passed stools (i.e. normal bowel movement) (18; 19). Each consistency category reflects differences in moisture. Decreased water is associated with longer transit time and less microbial growth due to lower nutrient mobility and enzyme activity (17). Bowel movement frequency in healthy adults (n= 124) was reported to range from 3 times per week to 3 times per day (19). Subjects that report at least one bowel movement per day will be recruited for ease of compliance with study protocol. In addition, the BSS form contains an extra column to capture information about menstruation during time of sample collections as this variable could impact metabolite or bacteria profiles .
- **Urine samples:** Subjects will be provided with sterile collection containers for collection of urine samples on days 2, 4, 6, 8, 10 and asked to keep samples in 4 °C fridge until transport to the IFNH laboratory to maintain metabolite stability (20). Subjects will be asked to bring their samples to the IFNH laboratory as soon as possible, within 2-3 days of collection, for processing. Urine samples will be aliquoted and stored at -80 °C until processing for metabolomics studies.
- **Blood sample:** On day 11 subjects will go to CAB to visit study nurses for a final blood sample draw (2 tablespoons or 30 mL). Blood will be used for CMP test and prepared serum will be aliquoted and stored at -80 °C until processing for marker analysis and metabolomics.

Table 1. Schedule of events and sample collections

Days	Screen	-5	0	2	4	6	8	10	11
Informed Consent	X								
Incl/Excl Criteria	X								
Med. History	X								
Height &Weight	X								
Clinic Visit	X		X						X
Blood Draw	X		X						X
Urine Sample		X	X	X	X	X	X	X	

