b) Urine samples (100 µL aliquots) will be centrifuged (10,000 g for 10 min at 4 °C) to remove particulates followed by dilution with water (1:1 to 1:3 vol/vol). Samples (10 µl) will be added to 10 ml of ACN and centrifuged at 3000 g for 15 min. The supernatant will be collected, dried, reconstituted in 500 µl of ethanol (50 % v/v) containing 0.1 % ascorbic acid and (w/v) and transferred to HPLC vials for untargeted analyte detection by high resolution MS (20; 35).

To deplete common matrix interferences such as phospholipids, salts, and proteins and optimize sample preparation each sample supernatant produced in a) and b) may also be loaded to Oasis Prime HLB Cartridges (Waters). Sample preparation methods will be tested.

2) Chromatographic separation and high-resolution mass spectrometry (MS): Triplicates (i.e. technical replicates) of each serum or urine sample will be separated on a Dionex UltiMate 3000 Binary Rapid Separation UHPLC with Diode Array Detector with a reverse phase (RP) C18 column for retention of medium polar and non-polar analytes as well as a hydrophilic interaction chromatography (HILIC) column for retention of highly polar metabolites (35). Separation of samples on RP and HILIC columns prior to MS will provide more comprehensive metabolome coverage. To detect the greatest number of metabolites, gradient elution protocols will be optimized separately for serum and urine samples. Chromatographic separations will be followed by MS using a Thermo Scientific Q Exactive Plus Orbitrap high resolution mass spectrometer. The orbitrap provides high mass accuracy (1–2 p.p.m.), resolution up to 100,000 and dynamic range of 5,000. Data will be collected in both positive and negative ESI modes (mass range of 100–2,000 m/z).

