4) Statistical analysis: To find the bacteria that respond to GP either positively or negatively (i.e. GP responders) we will omit those strains that are found to change with only SPI supplementation. To further understand how the GP responders affect host metabolic health as a group, we will derive a GP Responder

Index (GRI) based on the abundance and diversity [Heip evenness] of the identified bacteria (36). Data will be subject to two-way repeated measures ANOVA to decipher main effects and interactions between GP and SPI. $P < 0.05$ will be considered significant.

To detect significant differences in metabolites MetaboAnalyst 3.0 software (<http://www.metaboanalyst.ca/>) will be used. Principal components analysis (PCA) will transform original data variables into a smaller number orthogonal variables built from linear combinations to explain most of the data variance and cluster samples from each time-point or group to be analyzed. Significant difference ($p < 0.05$) will be determined within subject at different time-points, within group, and between groups. Variable importance in projection (VIP) scores will be estimated to select metabolites biomarkers from a partial least squares-discriminant analysis (PLS-DA). VIP scores are a weighted sum of PLS weights for each variable and measure the contribution of each predictor variable to the PLS-DA model. Compounds with VIP score > 4 represent metabolites with greatest change, which will be chosen for proof of identity. Before carrying out PCA and PLS-DA analyses, peak intensity will be controlled by a logarithmic transformation, and monitored by Pareto scaling. Methods for data preprocessing and statistical analysis will be optimized and additional corrections and tools will be applied as needed (37; 38).

Co-inertia analysis: To aid interpretation of the relationship between the bacterial responders and metabolomics datasets, they will be integrated using a multivariate method known as co-inertia analysis (CIA) (39). We expect to uncover bacterial species/strain level increases and decreases in GP-SPI-supplemented subjects that correlate with a concomitant increase and decrease in production of their metabolites.

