1.8 Specimen Collection

A. Primary Specimen Collection

▪ Types of Specimens:

Version Number: 3
Protocol Number: 2018002579
PI Name: [name]
Protocol Title: The Effect of Concord grape polyphenol-soy protein isolate complex (GP-SPI) on Gut Microbiota

RESERVED FOR IRB STAMP
DO NOT MODIFY THIS SPACE

Blood samples: A blood samples will be collected by study nurse at screening visit for CMP test. If CMP is within normal ranges, subject will be enrolled in study. Blood will be collected again at baseline (day 0) and at end of study (day 11). Each blood draw will be no more than 30 mL (2 tablespoons).

Stool samples: Subjects will be provided with Omnigene®Gut OMR-200 kits or collection tubes containing 95% ethanol and/or tubes containing 50% glycerol (50% water) along with paper toilet accessories (DNA genotek, Ottawa, Canada) for easy self-collection of a pea-sized amount of fecal sample. Each participant will be instructed on use of stool collection materials.

Urine samples: Subjects will be provided with sterile collection containers (100 mL) for self-collection of urine samples on same days fecal samples are collected and asked to keep samples in 4 °C fridge until transport to the IFNH laboratory to maintain metabolite stability (20).

▪ **Annotation:**

Blood samples: CMP tests will be performed on blood samples collected at screening visit, day 0, and day 11. Targeted and untargeted metabolomics analyses will be performed on de-identified blood samples collected on days 0 and 11 from participants enrolled in study.

Stool samples: Microbial community structure will be analyzed from de-identified fecal samples as previously described (51) and used for shot gun metagenomics studies.

Urine samples: De-identified urine samples will subject for targeted and untargeted metabolomics analyses.

▪ **Transport:**

Blood samples: Blood samples collected and processed by study nurse at Clinical Academic Building will be picked up by a study staff member of [name] lab and transported to IFNH on dry ice.

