6.0 Data Management Plan

6.1 Data Analysis

Statistical comparisons will focus on individual and aggregate comparisons with respect to baseline to follow-up change in gut microbiota populations and biochemistry profile in blood and urine samples.

For each outcome, the equality of the outcome means for GP-SPI versus SPI will be tested against a two-directional alternative, controlling the type 1 error at $\alpha = 0.05$. The analyses will be conducted using t-tests for between group analysis and with repeated measures to conduct analysis of variance. Post-hoc tests will be conducted for pairwise comparisons of GP-SPI and SPI employing the Tukey method for controlling the global comparison-wise significance at 0.05 level. Logarithms or other transformations will be applied for data seriously deviating from normality; alternatively, non-parametric analyses may be conducted.

Handling of missing data: The data will be analyzed using the procedures PROC MIXED and PROC GLIMMIX SAS (v 9.3 or later). Thus, mixed effects models for repeated measures will be employed to analyze all available data irrespective of missing or incomplete data attributable to dropouts or other phenomena. In anticipation of the possibility of missing data, we plan to conduct sensitivity analyses that compare our findings against protocol completer analyses and last observation carried forward analyses in addition to investigating characteristics of participants who fail to protocol.

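### Urine metabolites are compared across days with no named correction for how concentrated each sample is, and the bench dilution may vary two-fold, which costs precision and makes errors cluster across metabolites

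*Combined protocol and SAP*

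**What the plan says.** **Collection.** Section 1.3 states: "Subjects will be provided with sterile collection containers for collection of urine samples on days 2, 4, 6, 8, 10". The day -5 and day 0 samples bring the total to seven. Section 1.8 specifies "sterile collection containers (100 mL) for self-collection of urine samples on same days fecal samples are collected". No time of day, first-void rule, timed collection or volume measurement is given, so these are in effect spot samples.

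**Preparation.** In the metabolomics workflow of section 1.3, urine is centrifuged "to remove particulates followed by dilution with water (1:1 to 1:3 vol/vol"). Nothing says how the ratio is chosen, whether it is the same for all samples, or that it is recorded. The serum step includes an internal standard (taxifolin); the urine step lists none. The quality-control samples monitor instrument performance.

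**Analysis.** Under Statistical analysis in section 1.3, significance at p < 0.05 "will be determined within subject at different time-points, within group, and between groups". Section 6.1 also lists "baseline to follow-up change in gut microbiota populations and biochemistry profile in blood and urine samples". Before PCA and PLS-DA, "peak intensity will be controlled by a logarithmic transformation, and monitored by Pareto scaling". Creatinine, osmolality, specific gravity, total-signal and quotient normalisation are not mentioned anywhere.

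**The concern.** The peak for a metabolite in a spot urine reflects both how much was excreted and how dilute that void was. Bench dilution multiplies it again. Both act on the whole sample, so all its metabolites move up or down together.

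Urine metabolites are measured at seven time points, against two for serum. They feed the within-subject tests, the selection of biomarkers by PLS-DA, and the co-inertia analysis that links metabolites to bacterial changes. If the concentration factor stays in the data, real changes are harder to detect, and a chance difference in dilution can appear as many metabolite changes at once. Hydration could not be reconstructed later from the diary, because section 1.3 exempts water from it.

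**Working it through.** The plan gives no figure on this point to reproduce; its power statement in section 1.5 concerns *A. muciniphila* abundance.

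**1. Bench dilution.** Read as parts urine to parts water, 1:1 leaves 1/2 urine and 1:3 leaves 1/4. The ratio is (1/2)/(1/4) = 2. Read as 1 in n, the range is 3-fold.

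**2. Log and Pareto steps.** If sample i has concentration factor c_i, the log intensity of metabolite j is log(true_ij) + log(c_i). Pareto scaling centres metabolite j and divides by the square root of its SD across samples. The term log(c_i) is still there, in every metabolite of sample i. Dividing one metabolite by a constant does not change its t statistic.

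**3. Loss of precision.** From section 4.3: 30 enrolled less 6 non-completers = 24. Assumed, not in the documents: within-person metabolite log-SD 0.4; sample-to-sample log-SD of urine concentration h = 0.3, 0.5 or 0.7.

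- SD of the paired log difference = sqrt(2 × (0.4² + h²))
- Effective n = 24 × 0.4² / (0.4² + h²)

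| h | SD of difference | Effective n |
|---|---|---|
| 0.3 | 0.71 | 24 × 0.16/0.25 = 15.4 |
| 0.5 | 0.91 | 24 × 0.16/0.41 = 9.4 |
| 0.7 | 1.14 | 24 × 0.16/0.65 = 5.9 |

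With no concentration variation the SD would be sqrt(2 × 0.16) = 0.57.

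**4. Dilution unrelated to study day.** Simulation with no true change: 24 subjects, 300 metabolites, 300 repeats, paired t-test at 0.05 after log and Pareto. Assumed within-subject log-SD 0.5 and hydration log-SD 0.4.

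| Scenario | Mean share with p < 0.05 | 5th to 95th percentile across studies |
|---|---|---|
| No concentration variation | 5.1% | 3% to 7% |
| Random hydration | 5.5% | 0.3% to 18.7% |
| Random hydration and random 1:1 or 1:3 | 5.3% | 0% to 24% |
| Hydration and random dilution, each sample median-centred | 5.0% | 3% to 7% |

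The mean is close to nominal; the spread is not. Median centring stands in here for a per-sample concentration correction.

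**5. If concentration did differ by day.** Assume dosing-day urine is 10%, 20% or 30% more dilute, a log shift of ln 0.9, ln 0.8 or ln 0.7. Two-sided paired t-test, 23 df, noncentrality = sqrt(24) × shift / SD of difference, SDs as in step 3. Chance that a metabolite with unchanged excretion reaches p < 0.05:

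| h | 10% | 20% | 30% |
|---|---|---|---|
| 0.3 | 11% | 32% | 66% |
| 0.5 | 8% | 21% | 46% |
| 0.7 | 7% | 15% | 31% |

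Under the assumptions of step 4, log shifts of -0.1, -0.2 and -0.3 give 8%, 18% and 33%. If the two ends of the dilution range fell on different days, the figure would be 96%. Median centring, run for the -0.3 shift and for this last case, brought them to 5.0% and 4.8%.

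**The case against.** **The plan leaves room for a correction.** The sentence after the one on log and Pareto steps says preprocessing will be optimised and further corrections added where required. The workflow is introduced as an example, and the preparation text says methods will be tried out. The dilution range may therefore be a development range, with one ratio fixed later. This is fair, and it would remove the bench part. But no text commits to one ratio, no urine correction is named, and hydration would remain.

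**A reader might infer that supplement drinks dilute the dosing-day urine and so create an apparent GP-SPI effect.** The argument would be that participants "mix each packet of GP-SPI in 250 mL of water or in smoothie" twice daily on days 1 to 10, whereas day 0 is a break. The documents do not support that as a finding. SPI is taken the same way on days -5 to -1, and the day 0 sample follows those five days. If day 0 and dosing-day samples are all collected before the morning packet, recent supplement fluid is matched. The sample that does precede all supplement drinks is day -5. Because collection time is unstated, a day-linked difference is possible, but it is assumed in step 5, not shown. Its direction also matters: more dilute dosing-day urine gives apparent decreases and would mask true increases.

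**The extremes do not belong together.** The 66% figure needs h = 0.3, where effective n is 15. An effective n of 6 needs h = 0.7, where the same 30% shift gives 31%.

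**Weight.** This is a pilot whose primary endpoint is 16S composition. The related secondary endpoint is to collect and store samples for the MWAS. The log and Pareto sentence is also tied to PCA and PLS-DA, but no other pre-treatment is named for the univariate tests, so this does not help the plan.

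**Conclusion.** The omission is clear from the documents, and the named steps cannot make it good. Lost precision and errors shared across metabolites follow whenever sample concentration varies. Under the assumed SDs, 24 completers are worth about 15 down to 6 for a paired contrast. With dilution unrelated to day, false positives average near 5% but cluster, so one study may show almost none and another close to a fifth of null metabolites.

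Bias is conditional. It requires concentration or bench dilution to differ by study day, which the documents allow but do not establish. If dosing-day urine were 10% more dilute, the false-positive rate would be about 7 to 11%; at 30%, about 31 to 66%. Every SD and shift here is an assumption.

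The plan should be changed before the urine data are analysed. The matter is limited to the exploratory urine metabolomics and the MWAS that uses them; the 16S primary endpoint, the metabolic-panel safety endpoint and the serum results stand as they are.

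**What to change.** - **Urine preparation (section 1.3, Metabolomics Workflow).** Use one dilution ratio for all urine samples, or record each ratio and back-correct.
- **Statistical analysis (section 1.3).** Before the log and Pareto steps, normalise each urine sample to its own concentration. Either use the creatinine peak from the same MS run, or use probabilistic quotient normalisation against the pooled-urine quality-control sample already planned. Use the normalised values for all urine tests, PCA, PLS-DA and co-inertia.
- **Optional internal standard for urine.** If added before dilution it corrects bench handling only. It cannot correct for hydration and does not replace the normalisation.

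The cost is protocol wording and one processing step on data from the planned runs, with no new samples. Creatinine normalisation adds a little error of its own, which quotient normalisation can check.

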The proposed study will first investigate how short-term supplementation with GP-SPI may modify the gut microbial community in healthy participants while monitoring liver and kidney function/health. We will also perform a longitudinal, microbiome-wide association study (MWAS) to identify gut bacteria species/strains that are positively or negatively associated with GP-SPI supplementation. Metabolomics analysis will be performed on collected urine and blood samples to identify/quantify known and unknown metabolites. Shotgun metagenomic sequencing will be performed on fecal samples to generate high quality draft genomes for species/strain level identification. These dynamic data sets will serve as input for the MWAS to correlate increasing/decreasing levels of gut bacterial species/strains to increasing/decreasing metabolites in blood and urine. These bacteria-metabolite associations will then be used to infer cause-effect relationships that can be further tested *in vitro*. We expect that successful completion of these studies will contribute to mechanistic explanations for how dietary polyphenols such as grape PACs alter the gut microbiota and resulting MM to promote metabolic health.

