Overview: Using the deidentified fecal, urine and blood samples from Part 1 of above-described parent study, we will perform a MWAS. Healthy humans have unique gut microbial communities; however, we will investigate whether supplementation with GP will promote elements of similarity in the gut microbiota and resulting microbial metabolites (MM), including PAC-derived MM and host-derived MM such as secondary bile acids (BA), that could be linked to healthy states and metabolic resilience. Such data may reveal common ecological or functional rules existing in microbiotas of healthy individuals as well as GP- or host-derived MM biomarkers with diagnostic potential. Below is an example of a MWAS work flow.

Shotgun Metagenomics Workflow

gDNA will be extracted from deidentified fecal samples. Libraries will be constructed followed by high-throughput sequencing on an Illumina HiSeq instrument (Genewiz). Cluster generation, template hybridization, isothermal amplification, linearization, and blocking, denaturing and hybridization of the sequencing primer will be performed according to the workflow specified by service provider. Prinseq (23) will be used to trim and de-duplicate raw reads. Reads that align to the murine/human genome (24) will be removed.

De novo non-redundant metagenomic gene-catalogue construction and gene abundance-profile calculations: High-quality paired-end reads from each sample will be used for de novo assembly with IDBA_UD (25) into contigs of at least 500 bp. Genes will be predicted using MetaGeneMark (26). A non-redundant gene catalogue of microbial genes will be constructed with CD-HIT. Quality reads will mapped onto the gene catalogue using SOAPaligner (27). Aligned results will be sampled and downsized to an appropriate number of reads per sample.

Co-abundance gene groups (CAGs): Individual genes will be binned in to co-abundance gene groups (CAGs) with a canopy-based algorithm (28). Raw CAGs will be removed in the subsequent analyses if they have fewer than 3 genes or 90% of the total canopy profile is distributed in no more than three samples. CAGs with >700 genes will be regarded as bacterial CAGs for further analyses. The principal component analyses of the bacterial CAGs based on the Bray-Curtis distance and Procrustes will be performed with QIIME (29). Abundance of genes identified per sample will be determined to follow changes in gene richness over time course of GP-SPI supplementation.

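### The co-inertia step does not define its row unit or remove the participant effect, so if repeated samples are pooled, stable differences between people can appear as bacteria-metabolite links

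*Combined protocol and SAP*

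**What the plan says.** The integration gets one method sentence, in section 1.3, Metabolomics Workflow, item 4 (Co-inertia analysis): the bacterial responders and the metabolomics data are paired, and "they will be integrated using a multivariate method known as co-inertia analysis (CIA) (39". The paragraph expects to find "bacterial species/strain level increases and decreases in GP-SPI-supplemented subjects that correlate with a concomitant increase and decrease in production of their metabolites". Section 1.2 describes the same aim: "These dynamic data sets will serve as input for the MWAS to correlate increasing/decreasing levels of gut bacterial species/strains" with rising and falling metabolites in blood and urine. It adds that the associations will be used to infer cause and effect, for further testing in vitro.

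The inputs are repeated measurements:

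- **Stool:** section 1.3 has participants use the Bristol form and "complete it for stool samples they collect on days -5, 0, 2, 4, 6, 8, and 10 of the study", which is seven time points.
- **Urine:** section 1.8 specifies "self-collection of urine samples on same days fecal samples are collected", so also seven.
- **Serum:** section 1.8 limits serum metabolomics to days 0 and 11, so two.

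The MWAS overview in section 1.3 accepts that "Healthy humans have unique gut microbial communities". Nowhere does the plan say whether a row of the co-inertia tables is a sample, a participant mean or a change from day 0. It names no participant term, no within-participant centring and no permutation scheme for this step.

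**The concern.** Standard co-inertia analysis pairs two tables row by row and has no notion of which rows belong to the same person. If the rows are samples, each table mixes two kinds of variation: how people differ from one another at all times, and how each person changes. Only the second bears on the stated target.

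A bacterium and a metabolite that each differ stably between people can line up by chance across about 24 people. Seven repeats of each person then make that chance alignment look well supported. This would happen even if no sample were taken on GP-SPI, so it is a separate problem from the confounding of exposure with study day.

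At stake is the list of candidate producer-metabolite pairs that goes forward to cause-effect inference and laboratory work. Person-identity pairs could enter the list, and real within-person pairs could be masked.

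**Working it through.** The documents give no figure for this step, so there is nothing of the plan's own to reproduce. What follows is illustrative.

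**Inputs from the documents.** 30 enrolled and 20% expected loss (section 4.3): 30 − 6 = 24 completers. Stool-urine: 24 × 7 = 168 sample pairs. Stool-serum: 24 × 2 = 48.

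**Assumptions.** ICC of 0.3, 0.5 or 0.7, the same for bacterium and metabolite; independent residuals; no true link; a two-sided 5% test.

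**Pairwise correlation, pooled samples.** The variance of the correlation is inflated by about D = 1 + (T − 1) × ICC². The actual error rate of a nominal 5% test is then about 2 × [1 − Φ(1.96/√D)].

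| T | ICC | D | Approximation | Simulated, pooled | Simulated, centred |
|---|---|---|---|---|---|
| 7 | 0.3 | 1 + 6 × 0.09 = 1.54 | 11% | 11% | 5.0% |
| 7 | 0.5 | 1 + 6 × 0.25 = 2.50 | 22% | 21% | 4.4% |
| 7 | 0.7 | 1 + 6 × 0.49 = 3.94 | 32% | 33% | 5.1% |
| 2 | 0.3 | 1 + 0.09 = 1.09 | 6% | 6% | 4.9% |
| 2 | 0.5 | 1 + 0.25 = 1.25 | 8% | 8% | 5.4% |
| 2 | 0.7 | 1 + 0.49 = 1.49 | 11% | 11% | 5.2% |

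Simulations used 4,000 null data sets per row. The centred test uses n(T − 1) − 1 degrees of freedom. With 30 participants and T = 7 the pooled rates are nearly the same (12%, 22%, 33%).

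**Co-inertia itself.** With assumed tables of 15 bacteria by 50 metabolites, 24 participants, T = 7 and no true link, the pooled RV coefficient (overall agreement of the two tables) averages 0.14 at ICC 0. It rises to 0.19, 0.28 and 0.38 at ICC 0.3, 0.5 and 0.7. After centring it stays near 0.155 throughout. This distortion needs no significance test. If a test were added by shuffling samples freely, it would reject in 100% of null data sets at all three ICCs for T = 7, and in 47%, 99% and 100% for T = 2 (200 data sets, 199 permutations).

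**Loss of real links.** With an assumed true within-person correlation of 0.3, the pooled test finds it in 75%, 51% and 42% of runs at ICC 0.3, 0.5 and 0.7. The centred test finds it in 96%. At ICC 0.7 the pooled correlation has the wrong sign in 29% of runs.

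**What centring does not solve.**

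- *Shared time trend.* If two otherwise unlinked variables both rise by 1 residual SD by day 10 in everyone, the centred test is significant in about 35% of runs.
- *Permuting whole participants* keeps the day order, so a shared rise survives in every permuted data set. Under that common rise it rejected in about 6% of runs (ICC 0.5, 20 taxa by 50 metabolites). It therefore tests person-specific covariation, not the shared response.
- *Shuffling days within a person* rejected in 100% under the same common rise. It also rejected in 100% with a day-to-day autocorrelation of 0.5 and no link, where whole-participant permutation held 4% to 6%.
- *Change from day 0* cancels stable differences, but the five changes (days 2 to 10) share one day 0 value. With independent residuals they correlate at 0.5, so D = 1 + 4 × 0.25 = 2 and the error rate is 2 × [1 − Φ(1.96/√2)], about 17%, if they are treated as independent rows.

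**The case against.** The strongest reply is that the plan never says samples are pooled. Its language is about change: rising and falling levels here, baseline to follow-up change in section 6.1, and longitudinal comparison within each subject in section 1.5. A reader might infer from the co-inertia sentence that 168 samples will be counted as independent. The documents do not support that, because the row is simply undefined. If change from day 0 is meant, stable differences cancel. This stands, and it makes the point conditional.

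Second, the plan attaches no p-value or threshold to co-inertia, which serves to aid interpretation. The 5% level in that section belongs to the repeated-measures ANOVA and the metabolite comparisons. A reader might take 11% to 33%, or 100%, as this study's error rate. Those figures belong to tests assumed here, with assumed ICCs and table sizes. This also stands, although the RV inflation does not depend on any test.

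Third, the bacteria entering are responders, screened to exclude those that change with SPI alone. Screening for change does not remove stable differences in level, so the gap remains. But the calculations do not model the screening, so nothing here shows that the resulting list would mostly reflect who the people are.

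Fourth, this is a pilot, the listed MWAS endpoint is to collect and store samples, and the links are meant for in vitro testing. That limits the consequence to misdirected follow-up work.

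The other provisions do not fill the gap. The ANOVA in section 1.3 and the mixed models in section 6.1 compare outcome means. The within-subject wording in section 1.3 concerns metabolite differences. The clause allowing further corrections as needed is generic.

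**Conclusion.** The concern holds in conditional form. The plan names plain co-inertia for repeated samples aimed at a within-person target, without defining the row unit or removing the participant effect. If samples are pooled, differences between people that the protocol itself acknowledges can pass as bacteria-metabolite links. The illustrative size is 11% to 33% false positives per stool-urine pair and 6% to 11% per stool-serum pair at a nominal 5%, against about 5% after centring when there is no shared time trend. This rests on 24 completers, assumed ICCs of 0.3 to 0.7, independent residuals and an assumed test. The plan should be changed, but this is exploratory secondary work and the primary microbiota endpoint is not affected.

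**What to change.** In the co-inertia paragraph of section 1.3:

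1. State what a row is and which study days enter.
2. Run the integration on within-participant data: centre each taxon and metabolite within participant, or use change from day 0.
3. Report between-person links separately, labelled as not attributable to GP-SPI.
4. If p-values are given, never permute individual samples freely. Permute whole participants, and state that this tests person-specific covariation beyond any response shared by all participants. Say also that variables which merely share a time trend will correlate after centring.
5. For serum, pair the day 11 minus day 0 change with the stool day 10 minus day 0 change, because Table 1 schedules no stool on day 11.

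The cost is analysis wording and a few lines of code, with no new data. What is given up is that between-person associations leave the main integration.
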